## *CAESAR Study Protocol*

### *Stiffness verification testing*

We built a Caesar foot for each participant and obtained AllPro feet based on their respective size and weight category. Due to availability, these feet were a mix of 6- and 8-inch build heights, however. We tested each foot's stiffness at loads associated with running and walking using an ISO 10328 machine at College Park Industries (Figure 1). We quantified stiffness using a linear fit to the force-displacement curve and used this to verify similarity of stiffness categories between the two experimental feet (AllPro/Caesar). We quantified both absolute difference in stiffness and percent difference ( $100 * (\text{AllPro-CAESAR}) / ((\text{AllPro} + \text{CAESAR}) / 2)$ ).

### *Experimental Protocol*

This study was a repeated measures design of three prostheses: the Caesar foot, AllPro, and participants' prescribed walking and running feet. Each foot was tested on a separate day, with the order of testing randomized. In the CAESAR and AllPro sessions, a certified prosthetist fit and aligned the prosthetic foot. The participant then walked, jogged, and walked on stairs. The prosthetist made adjustments until both the participant and prosthetist were satisfied with the fit/alignment. This process took approximately 20 - 45 minutes.

For each session, participants arrived at the lab having fasted and avoided caffeine for a minimum of 4 hr. Participants first completed metabolic testing on a treadmill. Participants remained seated for 5 minutes, while a K5 portable metabolic system (Cosmed, Rome, Italy) measured their resting metabolic rate of oxygen consumption ( $VO_2$ , mL/kg/min). Participants then ran continuously for 5 min at a self-selected speed on a treadmill. If they were uncomfortable or unable to run for 5 minutes without significant hand support, they instead walked for 8 minutes at a fixed speed based on their leg length that approximately self-selected speed in this population (Gates et al., 2013).

Participants subsequently completed a series of ambulatory tasks including walking at a fixed speed based on leg length, walking at self-selected slow, comfortable, and fast speeds, walking up and down a 3-step instrumented staircase (Bertec, Columbus, OH), and walking up

and down a 7.5° ramp at self-selected speed. After each task, participants were asked to provide feedback on their comfort and stability on a 100-mm visual analog scale. During the CAESAR session, participants completed stair and ramp walking twice, once with the foot in ‘run’ mode and then with the foot in ‘walk’ mode. We then asked which mode they preferred for that task and why.

During all tasks, we tracked the motion of 49 reflective markers at 120 Hz using a 16-camera motion capture system (Qualisys AB, Gothenburg, Sweden) for the overground tasks or a 12-camera motion capture system (Qualisys AB, Gothenburg, Sweden) for treadmill tasks. Markers were placed on body landmarks including the C7, sternum, xiphoid process, T8, and bilaterally on the acromion, iliac crest, anterior and posterior superior iliac spines, greater trochanter, lateral and medial tibial epicondyles, lateral and medial malleoli, and 2nd and 5th metatarsals. Four-marker clusters were placed bilaterally on the thighs and shanks. For the amputated side, markers were placed on the socket and shoe, so they mirrored the intact side. For the prosthetic feet with a C or J running shape, two markers were placed on the medial and lateral sides of the most acute point on the prosthesis curvature (Buckley, 2000). For standalone running blades used without a shoe, one marker was placed on the most anterior point of the foot with two additional markers on the medial and lateral edges of the foot.

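### Does fitting activity described only for the CAESAR and AllPro sessions undermine the net VO2 comparison with the prescribed foot?

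*Combined protocol and SAP*

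**What the plan says.** Three prosthetic conditions are compared within participant. On scheduling, the Experimental Protocol says: "Each foot was tested on a separate day, with the order of testing randomized".

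Fitting is described for two conditions: "In the CAESAR and AllPro sessions, a certified prosthetist fit and aligned the prosthetic foot. The participant then walked, jogged, and walked on stairs". Adjustment of the foot went on until participant and prosthetist were both content. On duration: "This process took approximately 20 - 45 minutes". That figure includes the adjustments, so only part of it is exercise. For the prescribed-foot session the section neither describes comparable activity nor rules it out.

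The stated pre-test conditions are fasting and no caffeine for at least 4 hr. Then: "Participants first completed metabolic testing on a treadmill". The baseline is "Participants remained seated for 5 minutes, while a K5 portable metabolic system" recorded resting VO2, and the exercise follows: "Participants then ran continuously for 5 min at a self-selected speed on a treadmill". Those who could not run walked for 8 minutes instead. No recovery interval before the baseline is given.

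On set-up, the same section says "During all tasks, we tracked the motion of 49 reflective markers at 120 Hz" and "For the amputated side, markers were placed on the socket and shoe, so they mirrored the intact side".

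Under Data Analysis, net VO2 is the gross value over a 2-minute steady-state window minus the seated value. Under Statistical Analysis, metabolic results are given for individuals only and set against a published MDC where that is suitable.

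**The concern.** Subtracting a resting value assumes that rest means the same thing in every session. Here two sessions appear to begin with walking, jogging and stair climbing, and the third has no such activity described. If oxygen uptake had not settled when the seated measurement started, the subtracted value would be too high with CAESAR and AllPro, and net VO2 would look too low unless the same excess persisted into the exercise window.

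Randomizing the order of the feet does not help, because the activity belongs to the foot condition and follows it to whichever day it is assigned. With individual reporting there is also no averaging: each participant's reading rests on one baseline per session. At stake is whether a participant's change from the prescribed foot to an experimental foot is read as larger or smaller than the MDC.

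**Working it through.** The plan states no VO2 value, sample size or MDC, so there is no figure of its own to reproduce. The check has four steps.

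**1. The identity.** Net = gross − rest. Let fitting leave an excess d in resting VO2 and e in gross VO2. The net contrast of an experimental foot with the prescribed foot then shifts by e − d. Writing c = e/d, the shift is −(1 − c)d: the full −d at c = 0, half of it at c = 0.5, zero at c = 1, and of opposite sign at c = 1.5. Simple decay puts c between 0 and 1, since the exercise window comes after the baseline. Carry-over of another kind could exceed that, and the documents do not settle it. For CAESAR versus AllPro both sessions include fitting, so no systematic shift arises.

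**2. Was there a pause?** The text does not place fitting before the baseline in so many words, but a foot must be fitted before it is tested, and no separate fitting visit is described. Markers were tracked in every task, treadmill included, and some sat on the socket and shoe, so they could be final only after fitting. Seated rest leads straight into running, so marker and metabolic-system set-up probably came before the baseline. A pause is therefore likely; its length is not stated.

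**3. How size depends on the pause.** All inputs here are assumptions. Let the excess at the end of fitting be A = 3 to 7 mL/kg/min, decaying exponentially with constant tau = 1 to 5 min, and average over the full 5-minute baseline after a pause of w minutes:

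d = A × exp(−w/tau) × (tau/5) × (1 − exp(−5/tau)).

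For A = 7, tau = 5 the factor before decay is 7 × (1 − exp(−1)) = 4.425. For A = 3, tau = 1 it is 3 × (1/5) × (1 − exp(−5)) = 0.596.

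| Pause w (min) | d, adverse (A = 7, tau = 5) | d, mild (A = 3, tau = 1) |
|---|---|---|
| 5 | 4.425 × exp(−1) = 1.63 | 0.596 × exp(−5) = 0.004 |
| 10 | 4.425 × exp(−2) = 0.60 | about 0 |
| 15 | 4.425 × exp(−3) = 0.22 | about 0 |
| 20 | 4.425 × exp(−4) = 0.08 | about 0 |

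With no carry-over (e = 0) and an assumed MDC of 1.0 mL/kg/min, the adverse case exceeds the MDC after 5 minutes, is 22% of it after 15 (11% for an MDC of 2.0, 44% for 0.5) and 8% after 20 (4% and 16%). On an assumed rest of 3.5 and gross values of 12 (walking) and 30 (running), d = 0.2 is 0.2/8.5 = 2.4% or 0.2/26.5 = 0.8% of net VO2. The answer runs from material to nil, depending on a pause that the documents do not give.

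**4. Would a change help?**

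- *Equal seated recovery in all sessions.* If the prescribed-foot session has no prior exercise, its residual is about 0 whatever the wait, and the fitted sessions keep d. Equal waiting does not equalize the baselines; only a long enough wait or matched prior activity would. For d to fall below 0.15 (5% of an assumed rest of 3.0), the wait is ln(0.596/0.15) = 1.4 min in the mild case and 5 × ln(4.425/0.15) = 16.9 min in the adverse one. The protocol is also written in the past tense, so sessions were probably complete.
- *Repeating the comparison on gross VO2.* Gross contrast − net contrast = the between-session difference in rest, whatever its cause. A conclusion that changed could reflect ordinary day-to-day variation in rest as easily as fitting. The gross contrast keeps e, and it needs an MDC valid for gross VO2.
- *Listing resting and gross VO2 by session.* This lets a reader see any baseline difference. It corrects no estimate, and the commitment to report individual metabolic data does not exclude it.

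**The case for a change.** The strongest case for acting is that the mechanism needs no outside figure: any between-session difference in rest passes one for one into net VO2. The activity is tied to the foot, the recovery time is unstated, and the comparison with an MDC is made participant by participant, so a baseline difference could carry someone across the threshold unseen. The values needed to check this are already measured, so one table would cost almost nothing.

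The identity, the gap in the description and the limit of randomization all stand. So does the point that a short pause with slow recovery could matter. What does not stand is the step from a missing detail to a faulty result. The text does not say that the prescribed-foot session was free of warm-up activity, it supports a set-up pause, and it fixes neither the sign nor the size of any shift. The table is a fair request of the eventual report. It would not change how net VO2 is defined or computed, nor could it show that fitting caused a difference.

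**Conclusion.** No change to the plan is called for. The unstated recovery interval is a gap in description that set-up probably filled in practice; no wrong result is shown. The possible shift is confined to individual contrasts of CAESAR or AllPro with the prescribed foot, for an outcome with no test and no group estimate. Its size is unknown and possibly negligible: under the adverse assumptions above, at most 0.22 mL/kg/min after a 15-minute pause and 0.08 after 20.

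This rests on three readings: that fitting preceded the baseline on the same day, that each session's own rest is subtracted, and that marker and equipment set-up fell between fitting and baseline. If the pause were only about 5 minutes and recovery slow, the individual comparisons with the prescribed foot would deserve more caution. Even then, a few minutes of equal recovery would not cure the problem, and a gross-VO2 comparison could not identify its cause. Authors who wish to may state that rest is session-specific and show resting beside gross values; that is good reporting and optional.

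### Nothing says treadmill running speed was the same on each foot, yet net VO2, a per-minute rate with no speed term, may be related to MDC values

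*Combined protocol and SAP*

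**What the plan says.** All references are to the combined protocol and SAP.

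- **Design (Experimental Protocol).** There are three prosthetic conditions: "Each foot was tested on a separate day, with the order of testing randomized".
- **Metabolic test (Experimental Protocol).** In the part that describes every session: "Participants then ran continuously for 5 min at a self-selected speed on a treadmill". Those who could not run comfortably without substantial hand support had a fallback: "they instead walked for 8 minutes at a fixed speed based on their leg length".
- **Later tasks (Experimental Protocol).** The list includes "walking at a fixed speed based on leg length, walking at self-selected slow, comfortable, and fast speeds". Walking is therefore tested at both a fixed and a preferred speed. Running is described only at a preferred speed.
- **Feet compared (Experimental Protocol).** The third condition is the participants' "prescribed walking and running feet", and the marker set has a provision "For standalone running blades used without a shoe".
- **Derivation (Data Analysis).** Net VO2 is gross minus seated-rest VO2 over two minutes of steady state. The unit mL/kg/min is given beside resting VO2 and carries over by subtraction. There is no division by speed or adjustment for it.
- **Use (Statistical Analysis).** Metabolic results are individual data only. The reason given is that the type of activity varied. Changes are related to published MDC values where appropriate, but neither a criterion nor an MDC value is given.

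**The concern.** Oxygen uptake per minute rises with running speed even when the runner is no less economical. If a participant chose a faster speed on one foot than on another, the difference in net VO2 between the two days holds both the effect of the foot and the effect of the speed. A foot that lets someone run faster at equal or better economy could then appear to cost more oxygen.

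Reporting individual data does not remove this. The MDC comparison is made within a person across days, which is where a speed difference would enter.

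A speed difference is plausible if speed was chosen afresh each day, because the feet may differ in kind: two experimental feet against prescribed feet that may include running blades. The protocol also treats speed as worth fixing elsewhere, in the walking fallback and in one of the overground walking tasks.

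The running mechanics may share the problem. The Statistical Analysis section averages running over 30 s, and motion capture used "a 12-camera motion capture system (Qualisys AB, Gothenburg, Sweden) for treadmill tasks". The only other running described is during fitting of the two experimental feet ("The participant then walked, jogged, and walked on stairs"). The 30-s averages therefore probably come from the metabolic run. That is an inference, since the task list is not presented as complete.

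**Working it through.** The plan states no figure to reproduce: no speeds, net VO2 levels, MDC value or sample size. The check is a reading of all sections for any control of speed, followed by an illustration.

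**Reading.** The Experimental Protocol section fixes speed for the walking fallback and for one later walking task, and not for running. The Data Analysis section has no speed term in net VO2. The Statistical Analysis section does not mention speed as a normaliser, a covariate or a condition for using the MDC. No section says that treadmill speed was recorded.

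**Illustration (all inputs assumed).** Let net VO2 be proportional to speed to the power b, with b from 0.8 to 1.2, and let the foot have no effect on economy. Let d be the relative speed difference between two feet.

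- Shift in net VO2 = (1 + d)^b − 1
- Shift in cost per distance (net VO2 ÷ speed) = (1 + d)^(b − 1) − 1

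| d | Measure | b = 0.8 | b = 1.0 | b = 1.2 |
|---|---|---|---|---|
| 5% | Net VO2 | +3.98% | +5.00% | +6.03% |
| 5% | Cost per distance | −0.97% | 0 | +0.98% |
| 10% | Net VO2 | +7.92% | +10.00% | +12.12% |
| 10% | Cost per distance | −1.89% | 0 | +1.92% |

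In absolute terms, with b = 1 and an assumed net VO2 of 20 to 40 mL/kg/min, a 5% speed difference gives 20 × 0.05 = 1.0 to 40 × 0.05 = 2.0 mL/kg/min. Whether that exceeds the MDC cannot be judged, because no MDC value is given.

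**Can the direction reverse?** Take a constructed case: a foot that improves economy by 5% (factor 0.95) and is run 10% faster.

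- Net VO2: 0.95 × 1.10^b − 1 = +2.53%, +4.50%, +6.51% for b = 0.8, 1.0, 1.2. The foot looks worse.
- Cost per distance: 0.95 × 1.10^(b − 1) − 1 = −6.79%, −5.00%, −3.17%. The foot looks better.

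If d = 0, every shift due to speed is zero.

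**The case against.** The strongest reply is that silence is not a confound. A self-selected speed can be one preferred speed, found once and reused on all feet, just as well as a new choice each day. This stands: the documents fit both readings, and under the first there is no bias. A reader might infer that speeds did differ and that the VO2 comparison is confounded; the text does not support that.

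A second reply is that MDC values are used only where appropriate, on individual data, with no group test. This also stands in part. The documents do not say that pairs at different speeds were read against the MDC, and without an MDC value nobody can show that a reading would change. But the qualifier has no criterion, and the only source of variability named is type of activity, so it does not show that speed was dealt with.

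A third reply is that running at preferred speed is a fair test of a foot in use. Agreed. The difficulty lies only in reading a per-minute rate against an MDC when speeds are not known to match. For that reason net VO2 should stay in the report, with cost per distance set beside it.

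A reader might also infer that the running effect sizes are biased by a calculable amount. They are not: the source of the 30-s averages is inferred, and neither the standardiser for Hedges' g nor the sample size is stated.

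**Conclusion.** The point holds as a gap in specification with a real consequence if speed was chosen separately for each foot. As written, the plan allows a speed difference between feet to appear as a foot effect in net VO2, and nothing in the analysis would reveal it. Under the assumed exponents, a 5% speed difference alone moves net VO2 by about 4 to 6%, and dividing by speed reduces that to about 1% or less in either direction.

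The conclusion is limited in three ways. No speed difference is documented. It concerns only participants who ran. The percentages rest on assumed inputs and are not estimates for this study. It should be fixed because the remedy is nearly free and readers cannot otherwise tell which case applies. Confidence is medium.

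**What to change.** The protocol is written in the past tense, so the change is to analysis and reporting.

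1. State whether running speed was set once per participant or in each session.
2. List treadmill speed and activity (run or walk) by participant and foot.
3. For runners whose speed differed between feet, report net oxygen cost per distance as the metabolic comparison, with net VO2 beside it. The calculation is net VO2 in mL/kg/min divided by treadmill speed in m/min, giving mL/kg/m.
4. For runners, relate net VO2 changes to the MDC only for pairs of feet run at the same treadmill speed, and write this in as part of what makes the comparison appropriate.
5. If the 30-s running averages come from this run, say so and show the speed difference between feet beside the running effect sizes.

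If one speed was reused throughout, step 1 is a single sentence and steps 3 and 4 change nothing.

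**Cost.** Added speed and activity entries in a table and one division per foot for each runner whose speeds differed. Pairs at different speeds lose the MDC benchmark, and all of this depends on treadmill speed having been recorded. If it was not, that should be stated as a limitation on the running VO2 results.

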### *Statistical Analysis*

As there was variability in the type of activity performed during metabolic testing, we only report individual data and relate changes to reported minimal detectable change (MDC) values where appropriate (Davidson et al., 2016). For kinematic and kinetic measures, we first took the average across five strides for walking and 30-s for running. Due to the small sample size, we calculated effect size, as Hedge's  $g$  for these measures. These are interpreted as small for  $|g| \geq 0.2$ , medium for  $|g| \geq 0.5$ , and large for  $|g| \geq 0.8$  (Cohen 1988).

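### Does the plan need a rule for which CAESAR mode, run or walk, enters Hedges' g on stairs and ramp?

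*Combined protocol and SAP*

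**What the plan says.** The Experimental Protocol section describes a repeated measures comparison of three prostheses: CAESAR, AllPro and the participant's prescribed feet, each tested on its own day in randomized order. For stairs and ramp the CAESAR day differs from the others: "During the CAESAR session, participants completed stair and ramp walking twice". The first repetition used run mode and the second used walk mode. The one use the text gives for the repetition is a preference question: "We then asked which mode they preferred for that task and why". The same section adds: "During all tasks, we tracked the motion of 49 reflective markers at 120 Hz". Both CAESAR repetitions on stairs and ramp therefore produced motion data.

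The Statistical Analysis section is short. On averaging it says: "For kinematic and kinetic measures, we first took the average across five strides for walking and 30-s for running". It continues: "Due to the small sample size, we calculated effect size", meaning Hedges' g, read against bands starting at 0.2, 0.5 and 0.8. It names no mode and no pair of feet to be contrasted, and it gives no averaging rule specific to stairs or ramp.

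The Stiffness verification testing section says that each foot was bench-tested at running and walking loads to check that AllPro and CAESAR were similar. It refers to a Figure 1 and adds: "Due to availability, these feet were a mix of 6- and 8-inch build heights, however".

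**The concern.** The design treats CAESAR as one of three conditions, yet on stairs and ramp it yields two sets of data. A CAESAR-versus-AllPro g for those tasks could use run mode, walk mode, the mode each participant preferred, an average, or each mode in turn. These are different quantities, and a preferred-mode rule would mix modes across participants within one g.

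If the choice were made after seeing results, the reported g would tend to come from whichever mode did better by chance. Because g and its bands are the only analysis given for kinematic and kinetic measures, such a choice could move a result from one band to another.

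Two smaller points sit beside this. The text does not name the CAESAR mode used at each bench load, and it does not say whether build height differed within a participant's pair of feet.

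**Working it through.** The documents give no sample size, correlation, alpha or numerical result, so there is no figure of the plan's own to reproduce. The check has two parts: how large the effect of choosing a mode could be on assumed inputs, and whether the text calls for any such choice.

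**Counts.** Treating up and down separately, there are 4 stair and ramp tasks. With two modes, 4 × 2 = 8 possible g values per measure against one comparator, where a single-mode rule gives 4. Choosing the mode task by task allows 2^4 = 16 sets of four, or 2^2 = 4 if one choice covers both directions. These counts assume that g is computed on stairs and ramp against AllPro, which the Statistical Analysis section does not state.

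**Gain from picking the better mode, no true mode difference.** Let r be the correlation of a measure between CAESAR (either mode) and AllPro, and rm the correlation between the two modes. With equal variances, the two CAESAR-minus-AllPro differences correlate at

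ρ = (1 − 2r + rm) / (2 − 2r).

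- rm = r gives (1 − r)/(2 − 2r) = 0.5.
- r = 0.8, rm = 0.92 gives 0.32/0.40 = 0.8.
- r = 0.8, rm = 0.96 gives 0.36/0.40 = 0.9.

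With SE the standard error of one g, the SD of the gap between the two g values is SE × √(2(1 − ρ)). The mean gain from taking the larger is SE × √((1 − ρ)/π).

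| ρ (assumed) | SD of gap | Mean gain |
|---|---|---|
| 0.5 | 1.00 SE | 0.40 SE |
| 0.8 | 0.63 SE | 0.25 SE |
| 0.9 | 0.45 SE | 0.18 SE |

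**In units of g.** A simulation with r = rm = 0.8 and no true difference gives these mean values for the larger g:

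- n = 5: 0.122 (0.122/0.322 = 0.38 SE)
- n = 8: 0.095 (0.095/0.240 = 0.40 SE)
- n = 12: 0.074 (0.074/0.191 = 0.39 SE)

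All three lie below 0.2. The sample sizes are assumptions.

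**Band changes.** A second simulation (100,000 runs per setting; n = 5, 8, 12; r = 0.5 or 0.8; rm = 0.7 to 0.9; no true difference) gives a median gap between the two g values of 0.09 to 0.23, and different bands in 26% to 58% of runs. With one mode fixed in advance, |g| reaches 0.2 in 27% to 64% of runs; taking the larger |g| raises this to 40% to 82%. Setting by setting, the increase runs from 13 points (40 − 27; n = 12, r = 0.8, rm = 0.9) to 21 points (68 − 47; n = 5, r = rm = 0.8).

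So small-sample noise alone often produces a nominally small effect when the mode is fixed. Selection would add to that, but a mode rule would not remove the noise.

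**Does the text call for a selection?** Each task was done once in each named mode, and the preference question followed. Nothing says that preference decides which data are analysed, or that the modes are averaged. Two labelled conditions is the reading that needs no added assumption. Under it all eight values are shown and the gain in the table does not arise.

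**The case for a change.** The strongest case for a change is that the Statistical Analysis section is complete prose with nothing blacked out, that it is silent on mode, and that several readings fit. With small samples the two modes will often land in different bands. One sentence would settle the matter without new testing, because both modes were already recorded.

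The silence is real, and it extends further. If comfort and stability were rated after each repetition, those ratings have the same duplication. Run mode is also described as coming before walk mode, so a direct comparison of the two modes is mixed with order. Anyone setting the two g values side by side should keep this in mind.

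The step from silence to bias does not stand. It needs an analyst who picks the favourable mode, and the plan gives no favourable direction for kinematic or kinetic measures, no test and no primary endpoint. The document is also written in the past tense, so a rule added now would not be prespecification.

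The side points are weaker. Figure 1, which I have not seen, may show the bench mode, and running and walking loads map naturally onto run and walk modes. The build-height remark may concern only the AllPro feet, and no bias from it has been shown.

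**Conclusion.** No change to the plan is needed. The text omits a detail, but no rule it states gives a wrong result, and the natural way to fill the gap is to report each CAESAR mode under its own label, with preference described separately.

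The possible distortion, 0.18 to 0.40 standard errors of g, depends on a choice of mode that nobody proposes, and on equal variances, no true mode difference and assumed correlations. In g it is about 0.07 to 0.12 at n = 12 down to n = 5, with r = rm = 0.8.

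This conclusion rests on reading the two modes as separate conditions. It would change if a report gave a single CAESAR value for stairs or ramp without naming the mode, or used preference to choose it.

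### On stairs and ramp the CAESAR foot is always tested in run mode first and walk mode second, so mode preference cannot be separated from order

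*Combined protocol and SAP*

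**What the plan says.** The Experimental Protocol section describes the study this way: "This study was a repeated measures design of three prostheses". Each foot has its own test day, "with the order of testing randomized". This is the only randomisation in the document.

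Within the CAESAR day there is a second comparison, between the two modes of that foot. Both the stair task and the ramp task were repeated in that session, "once with the foot in ‘run’ mode and then with the foot in ‘walk’ mode". The preference question follows: "We then asked which mode they preferred for that task and why". The text gives one sequence, with no exception by participant or task.

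The Statistical Analysis section specifies no analysis of the preference answers. Its averaging rule ("we first took the average across five strides for walking and 30-s for running") does not mention stairs, ramp or mode, and no run-versus-walk-mode contrast is named. Comfort and stability ratings were collected after each task, but the text does not say whether they were taken separately for each mode.

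**The concern.** If every participant meets run mode first and walk mode second, mode and position are the same variable. A majority for walk mode may reflect the mode, the fact that it was the later and more recent pass, added practice, or a mixture. A majority for run mode may likewise reflect the mode, or fatigue or some other disadvantage of the second pass. Randomising the feet across days does not help, because it does not reach the order of modes within the CAESAR day.

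Preference is the only mode comparison the document names, and it is asked directly for each task, so readers will naturally take a majority as evidence about the modes. With one fixed sequence, that majority does not support a statement that one mode is preferred because of the mode itself. Any mode contrast in ratings, kinematics or kinetics would share the problem, if one were made.

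**Working it through.** The plan gives no figure to reproduce: it has no preference counts, sample size or order effect. The aliasing itself needs none of these. The illustration of its size does, and its inputs are assumptions.

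**1. Aliasing.** Take a model with an intercept, mode (run or walk) and position (first or second).

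- Fixed run-then-walk order: the design matrix has rank 2 of 3, and the correlation between mode and position is 1.0.
- Half the participants in each order: rank 3 of 3, correlation 0.

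This was checked with an illustrative 8 participants. The ranks do not depend on that number.

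**2. What a majority can mean.** Assumed quantities, none of them in the documents:

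- S: expected share choosing walk mode
- π: share choosing walk mode among participants who choose by mode
- f: share of participants who choose by position
- q: probability that a position-driven participant chooses the later pass

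In the fixed order, S = (1 − f)π + fq, so π = (S − fq)/(1 − f). Setting π = 0.5 gives the share of position-driven participants at which a majority is compatible with no mode preference among the rest: f = (S − 0.5)/(q − 0.5).

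| S | f needed, q = 1 | f needed, q = 0.8 |
|---|---|---|
| 0.60 | 0.10/0.5 = 20% | 0.10/0.3 = 33% |
| 0.625 (e.g. 5 of 8) | 0.125/0.5 = 25% | 0.125/0.3 = 42% |
| 0.75 (e.g. 6 of 8) | 0.25/0.5 = 50% | 0.25/0.3 = 83% |

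The same figures apply to a run-mode majority, with q replaced by 1 − q.

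**3. Bounds.** If q may lie anywhere from 0 to 1, π lies between (S − f)/(1 − f) and S/(1 − f), cut to the range 0 to 1. For S = 0.625:

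- f = 0.10: 0.525/0.90 to 0.625/0.90, that is 58% to 69%
- f = 0.25: 0.375/0.75 to 0.625/0.75, that is 50% to 83%
- f = 0.50: 0.125/0.50 to 1, that is 25% to 100%

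**4. Effect of counterbalancing.** In equal order groups with the same f and q, the run-first share is (1 − f)π + fq and the walk-first share is (1 − f)π + f(1 − q). Their unweighted mean is (1 − f)π + f/2, so the mean minus 0.5 equals (1 − f)(π − 0.5). Its sign is that of the mode-driven preference for any f below 1.

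Example: π = 0.4, f = 0.5, q = 0.7. The fixed order gives 0.20 + 0.35 = 0.55, a majority in the wrong direction. The walk-first group gives 0.20 + 0.15 = 0.35, and the mean of the two is 0.45.

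**5. Numeric contrasts, if any are made.** Let m be the mode effect, o an additive order effect, and cR and cW the carryover from run and walk mode. The expected walk-minus-run difference is m + o + cR in run-first participants and m − o − cW in walk-first participants. The fixed order passes o in full into the estimate. The unweighted mean of the two groups is m + (cR − cW)/2: the order effect is gone, but unequal carryover remains.

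**The case against.** The strongest reply is that little rests on this item. The study compares three feet in randomised order. Mode preference is one follow-up question with an open reason, and no test, summary or conclusion is attached to it. **This stands**, and it limits the weight of the point. A descriptive majority is still open to the causal reading that the design cannot support.

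A second reply is that participants were not new to the foot. The fitting included walking, jogging and stairs ("This process took approximately 20 - 45 minutes"), and the treadmill test and level walking are listed ahead of stairs and ramp ("Participants subsequently completed a series of ambulatory tasks including walking at a fixed speed based on leg length"). This may reduce a practice effect. It does not break the aliasing: no ramp practice is listed in the fitting, the mode used is not stated, and recency or fatigue could remain. The reasons participants gave help interpretation in the same limited way.

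Third, both tasks used the same mode order. If preference differed between stairs and ramp, an order effect common to both could not explain the difference. **This is correct under that assumption**, but it answers a different question from which mode is preferred on a given task.

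Fourth, the inputs to the illustration are assumed, and overturning a 75% majority takes 50% to 83% of participants choosing by position. Sampling error is also large: 6 of 8 has an exact 95% interval of 35% to 97%. **Both statements are true.** Sampling error is a separate limit that counterbalancing does not remove; equally, a larger sample would not remove the aliasing.

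Finally, the text is in the past tense, so the design may no longer be open to change. In that case only the reporting can change.

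**Conclusion.** The concern holds as written. With one fixed mode sequence, each task's mode preference is completely aliased with position, and these data alone cannot separate the two. That follows from the sequence and requires no assumption that an order effect occurred; its existence, direction and size are unknown.

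The practical size can only be illustrated. Under the assumed model, a 60% to 75% majority is compatible with no mode preference among mode-driven participants when 20% to 50% choose by position, if all of them choose the same position. The required share rises to 33% to 83% if only 80% of them do. The statement that counterbalancing restores the right direction assumes equal groups with the same f and q in each, and concerns expected shares, not the result in a small sample.

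The point concerns the two modes within the CAESAR day. It does not call into question the randomised order of the three feet. It should be addressed because it limits what may be concluded about the modes.

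**What to change.** **If the mode order did vary in practice:** correct the sentence in the Experimental Protocol section and report the order each participant followed.

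**For data collected in the fixed order:** report mode preference, and any mode differences, as descriptive and confounded with order. Set the recorded reasons beside them. Draw no conclusion that a mode is better, or preferred, because of the mode itself. The cost is a limitation statement and a restated conclusion.

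**For any session still to be run (the document indicates none):** randomise or alternate mode order between participants in equal numbers, and record it. Report preference by order group with the unweighted mean of the two group shares. For any numeric contrast, report the unweighted mean of the two groups' walk-minus-run differences, and state that unequal carryover is not removed.

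This adds no passes; it needs an order list and one recorded field. The document does not say how the mode is switched or by whom, so I assume that starting in either mode takes similar effort. With group sizes a and b and n = a + b, the variance of the order-balanced mean difference relative to the raw mean is (n/4)(1/a + 1/b). This is 1.000 for equal groups, 1.0125 for 5:4, 1.0208 for 4:3 and 1.0417 for 6:4, so the loss of precision is at most about 4% for these illustrative splits.
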